12.4.2 Content of statistical analysis

The main analysis includes:

(1) Distribution of cases between the two groups: Comparing total abscission rate and abscission rate due to adverse events.

(2) Comparability analysis: Comparison of demographic data and other baseline indicators to measure comparability between the two groups.

(3) Compliance analysis: To compare whether the two groups of patients were using the test drugs on time and on time, and the drugs that were not banned in the unused regimen.

(4) Validity analysis: both PP and ITT analyzed the main efficacy indicators; since this study is a multicenter clinical trial, the effects of central effect and baseline on efficacy indicators should be considered.

The incidence of delirium was compared by chi-square test, chi-square test, CMH chi-square test, delirium exacerbation analysis, H analysis of data consistent with normal distribution; otherwise, H test, single-factor analysis of delirium aggravation, The data that do not conform to normal distribution are tested by rank sum test or Kruskal-Wallis test (H test).

(6) Safety analysis: First of all, according to the requirements of the correlation of adverse reactions, the list describes the adverse events and adverse reactions in the two groups (including the number of cases of various adverse events, the number of cases of "normally abnormal" before and after the test and the rate of variation). The adverse reactions were statistically analyzed by the chi-square test.

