11.1 Adverse events

11.1.1 Definition of adverse events and reactions

Adverse events (Adverse Event, AE) refer to any adverse symptoms, abnormal signs, and abnormal laboratory results after the intervention study, whether there is a causal relationship with the intervention. Any adverse events, including those provided by the subjects voluntarily or obtained through inquiry by the researcher or by physical examination, laboratory examination, or other examination methods, should be recorded on the CRF and actively handled, followed closely until remission or condition is stable.

Adverse reactions (Adverse Drug Reaction, ADR): harmful, rather than desirable, results in a causal relationship with drug use during the normal application of the drug at the prescribed dose.

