11.1.2 Records of adverse events

(1) All adverse events must be tracked, and the researcher must record them in the corresponding section of the case report form and record the adverse events in detail.

(2) Adverse event content: name of symptom or sign or diagnostic name of disease or laboratory examination of an indicator abnormality.

(3) Date of onset of adverse events: date of the first occurrence of AE or related symptoms AE subjects.

(4) End date of adverse events: date of cessation of AE or AE-related symptoms. If the AE still exists, do not fill in the end date.

(5) Evaluation of the severity of adverse events

Mild: symptoms and signs present, but can tolerate, generally without treatment

Moderate: Symptoms or signs cause discomfort, daily activities are limited, appropriate treatment can be taken

Severe: no ability to work and daily activities, need active treatment

(6) Measures taken :discontinuation of the relevant medication or treatment ; use of therapeutic measures; and no measures are taken.

(7) Result of adverse events: persistence, improvement, mitigation

(8) Evaluation of the correlation between adverse events and anesthesia:

Five-level evaluation criteria:

Positive correlation: adverse events appear under a reasonable time order after anesthesia;

The anesthetic method used to explain adverse events is more reasonable than other causes;

The pattern of adverse events is consistent with the pattern of adverse reactions caused by such anesthesia.

Maybe relevant: adverse events appear under the reasonable time order after anesthesia;

The use of anesthesia to explain adverse events is more reasonable than other causes; but do not rule out other reasons.

It may not be relevant: the occurrence of adverse events does not conform to the reasonable time order after anesthesia; (Other causes may cause adverse events, but the possibility of anesthesia can not be ruled out;None: The possibility of adverse events resulting from or excluding from anesthesia by other causes);

Can not be determined: the occurrence of adverse events does not conform to the reasonable time order after anesthesia; However, it is impossible to determine whether it is related to anesthesia, nor can it be explained by other reasons.

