6.2 Baseline Characteristics

Categorical data will be summarised by frequencies and percentages. Continuous data will be summarised by the number of responses, mean and standard deviation if deemed to be normally distributed, and the number of responses, median and interquartile range or total range if data appear skewed. Tests of statistical significance will not be undertaken, nor confidence intervals presented ⁷.

7. Statistical Analysis

7.1 Primary outcome:

The primary outcome is the incidence of postoperative delirium during 7 postoperative days, diagnosed with the Confusion Assessment Method, and will be a categorical variable.

7.2 Secondary outcome measures are as follows:

- The subtype, severity, and duration of delirium in 7 days after the surgery, diagnosed with the Delirium Rating Scale-Revised-98 and confusion Assessment Method, subtypes and duration of delirium are categorical variables, and severity score is a continuous variable;
- Duration of delirium, measured by days from the onset of delirium symptom to the resolution of symptoms, which is a continuous variable;
- The intensity of postoperative pain, measured with acute pain score in 7 days after the surgery using Visual Analogue Scale (VAS), which is a continuous variable;
- The occurrence of non-delirium in-hospital complications within 30 days after surgery, including chest infection, myocardial infarction, renal failure, gastrointestinal ileus, which is a categorical variable;
- Length of hospital stay, measured by the sum of inpatient days from admission to discharge, which is a continuous variable;
- Mortality during the hospital stay and during the follow-up period after hospital admission, which is a categorical variable;
- Incidence of delirium in the clinic or at the residence on 30-day, 6 months, 12 months after surgery, diagnosed with CAM, which is a categorical variable;
- Cognitive and functional decline on 30-day, 6 months, 12 months after surgery, diagnosed with Mini-Mental State Examination (MMSE) and Hospital Anxiety and Depression Scale, which is a categorical variable;
- Quality of life on 30 days, 6 months, 12 months after surgery, using 36-Item Short Form questionnaire, which is a categorical variable;

- Economic parameters, including total cost in hospital and expenditure for anesthesia and resource using costs, including equipment and disposables required for each anesthetic technique, which are the continuous variables.

8. Analysis Methods

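### The one laboratory-specific safety summary appears to be an ungraded normal-to-abnormal count, so worsening from an already abnormal preoperative value shows only if reported as an adverse event or complication

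*Protocol*

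**What the plan says.** **Data collected.** Protocol section 10, Table 1, schedules haemoglobin, alanine aminotransferase, albumin, urea nitrogen, creatinine, blood gases, electrolytes and oxygen saturation before surgery and on each of P1 to P7. That is up to eight values per measure per patient.

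**Planned safety summary.** Protocol 12.4.2(6) describes a listing of adverse events and adverse reactions by group, "including the number of cases of various adverse events" and also "the number of cases of 'normally abnormal' before and after the test and the rate of variation". It gives no reference limits, grades, category for abnormal values that get worse, or change from baseline. The test named is for reactions: "The adverse reactions were statistically analyzed by the chi-square test".

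**Adverse events.** Protocol 11.1.1 defines these to include "any adverse symptoms, abnormal signs, and abnormal laboratory results after the intervention study". Protocol 11.1.2 allows the recorded event to be a "diagnostic name of disease or laboratory examination of an indicator abnormality". Severity is graded clinically; the lowest grade reads "Mild: symptoms and signs present, but can tolerate, generally without treatment".

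**Organ complications.** Renal failure is a named secondary outcome in Protocol section 9. SAP 7.2 lists "chest infection, myocardial infarction, renal failure, gastrointestinal ileus, which is a categorical variable". SAP 8.2 (SO4) summarises these complications by arm and rules out a relative effect estimate.

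**SAP.** It contains no analysis of laboratory values. Protocol 12.4.3 lists covariance analysis and rank tests for continuous data in general, without assigning them to laboratory measures.

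**The concern.** A normal-to-abnormal count has two built-in limits. A patient whose preoperative value is already outside the normal range cannot enter it, however much the value worsens. Among patients who can enter it, a small movement across the limit counts the same as a large one, and a large rise that stays within the limits does not count at all.

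Eligible patients are aged 65 or over, ASA I to IV, with an acute hip fracture, so abnormal preoperative values are plausible and those patients may be the more vulnerable ones. The stake is the laboratory safety comparison between regional and general anaesthesia. It could look more balanced than the underlying data, although the repeated measurements that would show a difference are already being collected.

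**Working it through.** The documents state no figure for laboratory safety, so there is none to reproduce. The 441 per group in SAP 3.3 is for delirium and has no bearing here. The check has two parts: what each planned route can register, and how large the effect could be under stated assumptions.

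**1. Which route registers which patient**

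- *Normal before, abnormal after:* counted under 12.4.2(6), whatever the size of the change.
- *Abnormal before, worse after:* not counted under 12.4.2(6). It can enter as an adverse event, since 11.1.1 does not require a normal baseline, or as a complication if one is diagnosed.
- *Abnormal before, unchanged after:* read literally, 11.1.1 makes this an adverse event too. The adverse event count therefore does not separate deterioration from a long-standing abnormality.
- *Normal before, large change within limits:* neither counted as a shift nor an abnormal laboratory result.

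The severity grades in 11.1.2 rest on symptoms, function and need for treatment, so they do not measure the laboratory change.

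**2. Illustration: share of worsenings the count omits**

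Let f be the fraction abnormal before surgery and r their risk of worsening relative to patients with normal values. Neither is in the documents; both are assumptions.

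Share omitted = f·r / (f·r + 1 − f)

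- f = 0.2, r = 1: 0.2 / (0.2 + 0.8) = 0.20
- f = 0.5, r = 1: 0.5 / (0.5 + 0.5) = 0.50
- f = 0.2, r = 3: 0.6 / (0.6 + 0.8) = 0.43
- f = 0.5, r = 3: 1.5 / (1.5 + 0.5) = 0.75

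This is the share omitted by the count alone, before adverse event reporting recovers any of it.

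**3. Illustration: dilution by trivial crossings**

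Assume true worsening of 10% in one arm and 5% in the other (ratio 2.0), the same risk whatever the baseline, every true worsening from a normal value crossing the limit, and a fraction t of the remaining normal patients crossing trivially. With f abnormal at baseline, the counted proportions are:

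- higher-risk arm: (1 − f)(0.10 + 0.90t)
- lower-risk arm: (1 − f)(0.05 + 0.95t)

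The factor (1 − f) cancels in the ratio:

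- t = 0: 0.10 / 0.05 = 2.0
- t = 0.05: 0.145 / 0.0975 = 1.49
- t = 0.10: 0.19 / 0.145 = 1.31

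So under these assumptions, leaving out baseline-abnormal patients loses events without changing the ratio, while trivial crossings pull the ratio towards 1.

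**The case against.** **The count is not the only route.** A reader might infer that deterioration from an abnormal baseline is never counted. The documents do not support that. The same sentence of 12.4.2(6) counts adverse events, and 11.1.1 and 11.1.2 make an abnormal laboratory result recordable whatever the baseline. This stands, and it narrows the gap. It does not close it: that route depends on the event being entered, does not isolate worsening, is graded on clinical grounds, and leads to a stated test only for events judged to be reactions.

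**Renal harm is reported separately.** A reader might also infer that the plan would hide a renal injury. Renal failure is a named outcome in both documents and is summarised by arm, so a diagnosed failure would be seen. What remains is worsening short of a diagnosed complication and not entered as an adverse event. For the diagnosed cases, SO4 gives no effect estimate.

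**The wording is garbled.** The phrase in 12.4.2(6) does not mention laboratory tests, and it might mean numbers normal and abnormal at each time, or a rate of change. This is a fair caution. Numbers abnormal before and after would still not move when an abnormal value worsens. If a rate of change in values was meant, no measure, comparison or baseline adjustment is stated.

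**Power.** It is tempting to turn the dilution into a loss of power. No test of this count is planned, and the trial is sized on delirium, so a power figure would describe an analysis that the documents do not contain.

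**Conclusion.** The point holds as a reporting gap. On the most natural reading, the only laboratory-specific summary is ungraded and takes no account of how far a patient's value moves from its own baseline. The SAP does nothing to supplement it. Worsening from an abnormal preoperative value is seen only through adverse event reporting or a diagnosed complication.

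The size is unknown. The 20% to 75% omitted, and the fall in the ratio from 2.0 to between 1.31 and 1.49, are illustrations that rest entirely on assumed inputs. They show the direction of the effect and that it could be material; they are not estimates for this trial. The documents do not support a claim that organ harm would go undetected, and nothing here touches the delirium analysis or the sample size.

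**What to change.** Amend Protocol 12.4.2(6) and carry the same text into the SAP:

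- **Shift table.** Replace the count with a full table from the preoperative value to the worst value on P1 to P7, by randomised arm, showing every cell and including a category for abnormal values that become worse. State the reference limits and how worse is defined.
- **Baseline-adjusted comparison.** For creatinine (highest P1 to P7 value, log scale), haemoglobin and oxygen saturation (lowest P1 to P7 value), report the between-arm difference adjusted for the preoperative value by ANCOVA, with a 95% confidence interval.
- **Data available.** Show the number of postoperative values per arm. A worst value depends on how many were taken, and patients discharged before P7 have fewer.
- **Thresholds.** The documents contain no creatinine-ratio threshold. If one is to be reported as well, the sponsor should choose it before unblinding.

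The cost is protocol and SAP wording and a few extra descriptive safety tables from data that Table 1 already collects. No new measurement is needed and patient care does not change.

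### The only named test of adverse-event occurrence is on causality-attributed adverse reactions, a term the protocol defines inconsistently; all-cause adverse events and serious adverse events have no planned between-arm test or estimate

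*Protocol*

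**What the plan says.** Protocol 12.4.2(6) handles harms in two steps. First, "the list describes the adverse events and adverse reactions in the two groups", with counts. Then: "The adverse reactions were statistically analyzed by the chi-square test". It names no test or effect estimate for adverse events of any cause, or for serious adverse events (SAEs).

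Three passages bear on what an adverse reaction is:

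- Protocol 11.1.1 gives a drug-based definition: "harmful, rather than desirable, results in a causal relationship with drug use during the normal application of the drug at the prescribed dose". By contrast, an adverse event is any untoward finding after the intervention, irrespective of cause.
- Protocol 11.1.2(8) sets a five-level scale headed "Evaluation of the correlation between adverse events and anesthesia". One criterion for the highest grade reads "The anesthetic method used to explain adverse events is more reasonable than other causes".
- Protocol 12.4.2(6) invokes the correlation requirements for adverse reactions, but does not say which grade or grades qualify an event as one.

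On who judges, Protocol 11.1.2 says that the researcher records events. It does not describe a masked causality rating. The only masking-type measure, in Protocol section 10, keeps the delirium assessor and data collector unaware of the study's design and purpose; allocation is not mentioned.

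Harm also appears elsewhere. Protocol 12.4.2(1) compares dropout due to adverse events. Protocol section 9 lists named complications and mortality as secondary outcomes. SAP 4.6 puts safety outcomes under intention-to-treat. SAP 8.2 (SO4) summarises complications by arm and states that no relative effect will be calculated, although Aim 4 in SAP 2.2 is to compare them. SAP section 8 ends at SO5, with no entry for mortality, adverse events or SAEs.

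**The concern.** This is a comparison of two anaesthetic techniques, and the grading criteria ask the rater to weigh the technique as an explanation. A rater who applies them as written needs to know which technique was used. The count of reactions is then the product of two things: how often events occur, and how readily they are blamed on that anaesthetic. If the second factor differs between arms, the chi-square test compares a mixture of harm and expectation. It can show a difference where harm is equal, or show none where harm differs.

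The definition adds a separate uncertainty. On the wording of 11.1.1, a purely procedural injury, such as one from a puncture or an airway device, would not be a reaction because no drug caused it. On the wording of 11.1.2(8), it could be. The tested endpoint is therefore not fixed in advance.

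**Working it through.** **Inputs.** The documents give no event rate, attribution rate or power for the safety comparison. The per-arm numbers come from SAP 3.3: 441 per group required, 1000 in total at 1:1. All event and attribution rates below are assumptions.

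**The plan's own figure.** With 26% versus 0.70 × 26% = 18.2%, two-sided 5% and 80% power, the unpooled formula gives (1.960 + 0.842)² × (0.26×0.74 + 0.182×0.818) / 0.078² = 440.3, so 441 per group. It reproduces. It concerns delirium and is used here only as a realistic arm size.

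**Creating a difference, 441 per arm.** Expected reactions = event rate × attribution probability × 441. With equal arms, N = 882, and a and b reactions, the uncorrected chi-square is (a−b)² × N / [(a+b)(N−a−b)]. The corrected one replaces |a−b| by |a−b|−1. The true event rate is equal in both arms.

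| Event rate | Attribution | Expected reactions | Rounded | Uncorrected p |
|---|---|---|---|---|
| 15% | 40% vs 20% | 26.5 vs 13.2 | 26 vs 13 | 0.033 |
| 15% | 40% vs 25% | 26.5 vs 16.5 | 26 vs 16 or 17 | 0.11 to 0.16 |
| 15% | 40% vs 30% | 26.5 vs 19.8 | 26 vs 20 | 0.36 |
| 10% | 40% vs 20% | 17.6 vs 8.8 | 18 vs 9 | 0.079 |

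First row in full: 13² × 882 / (39 × 843) = 4.53, p=0.033. Corrected: 12² × 882 / (39 × 843) = 3.86, p=0.049.

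**Chance of a significant result, 500 per arm, two-sided 5%, equal true event rates.** Power = Φ{[√n·|p₁−p₂| − 1.96·√(2p̄(1−p̄))] / √(p₁(1−p₁)+p₂(1−p₂))}, where p₁ and p₂ are event rate × attribution.

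| Event rate | Attribution 50% vs 40% | Attribution 50% vs 30% |
|---|---|---|
| 10% | 12% | 36% |
| 20% | 20% | 65% |
| 30% | 28% | 83% |

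**Hiding a difference, 500 per arm, true event rates 30% vs 20%.**

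- All events: 30% vs 20%, power about 96%.
- Equal 50% attribution: 15% vs 10%, power about 67%. Testing a subset loses power even without bias.
- Attribution 40% vs 60%: 0.30×0.40 = 12% and 0.20×0.60 = 12%. The tested rates are equal, so the chance of significance falls to the nominal 5%.

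**The case against.** The strongest reply is that safety inference does not rest on this test alone. All adverse events are tabulated by group, so a marked all-cause imbalance would be visible. Dropout due to adverse events is compared. The named complications and mortality need no attribution, and Protocol 12.4.3 offers general chi-square and Fisher methods for count data. That is correct, and it rules out saying that no other harm comparison exists. It does not fill the gap: dropout measures discontinuation rather than occurrence, SO4 calculates no relative effect, SAP section 8 has no mortality method, and the general methods are not tied to all-cause events.

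A reader might infer that technique-related harm is definitely outside the tested set. The documents do not support that. It follows from 11.1.1 taken alone, but 11.1.2(8) uses the term for reactions caused by anaesthesia, and it is the only correlation scheme to which 12.4.2(6) could be referring. What stands is an inconsistency.

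A reader might also infer that the five grades leave events with plausible timing but a better alternative cause unclassified. The text there is garbled, and it includes a grade of none, concerning other causes, with no timing condition attached. That reading should not be pressed.

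That raters know the anaesthetic is an inference from the criteria and from the absence of stated masking, not something the protocol says. Finally, the two-fold attribution imbalance is assumed, and milder imbalances lose significance, as the first table shows.

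**Conclusion.** The point holds in limited form. In the safety analysis, the one named test of event occurrence is on an attributed endpoint whose definition varies between sections, and neither document plans a between-arm test or estimate for all-cause adverse events or SAEs.

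The arithmetic shows that distortion is possible in either direction, not that it is expected. Under the assumed rates at 500 per arm, the chance of a spurious significant difference runs from about 12% to 83%, and a real difference detectable with 96% power can vanish entirely. These figures rest on attribution differing between arms, on which the documents are silent. The primary outcome is unaffected. This is a worthwhile, inexpensive improvement to the safety analysis.

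**What to change.** 1. In Protocol 12.4.2(6), and as a new entry in SAP section 8, compare the proportion of patients with any adverse event and with any SAE by randomised arm, regardless of attributed cause, each with a risk difference and 95% CI.
2. Report attributed events by arm descriptively, without a test.
3. Reconcile Protocol 11.1.1, 11.1.2(8) and 12.4.2(6): use one causal term covering both the anaesthetic procedure and the drugs, and state which grades count as attributed.

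The cost is wording only, because the protocol already requires all adverse events to be recorded on the case report form. The downside is dilution: unrelated background events in older patients add noise. Since 11.1.1 counts abnormal laboratory results and Table 1 schedules blood tests daily, the proportion with any adverse event may be high, and the SAE comparison may then be the more informative of the two.

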12.4.3 Statistical analysis methodology

Metrological data: First, the normal test is carried out, and the methods of t-test, pairing t-test, variance analysis, covariance analysis are used for those that conform to a normal distribution, and rank-sum test, paired rank-sum test, H test and so on are used for the data that do not conform to normal distribution.

Numbering data: using calibration chi-square test, Fisher accurate test, etc.; grade data using Ridit analysis, CMH method.

(3) Multi-center analysis of comprehensive efficacy: counting data using CMH method; measurement data using covariance analysis.

All the statistical tests were bilateral, and the P-value was less than or equal to 0.05.

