are used for surgical or other reasons, please record them in detail.

- 4) Intraoperative anesthesia management: if the anesthetic effect of the local anesthesia group can not complete the operation, the anesthesiologist can decide to use the drug or change the general anesthesia and record it in detail. This study does not make any provision for this situation. The general anesthesia group adjusted the depth of general anesthesia according to the surgical stimulation. Blood pressure reduction base value 30% or systolic blood pressure less than 90 mmHg is hypotension, recommended for vasoactive drugs or liquid treatment, the anesthesiologist can be appropriate according to personal experience.
- 5) Postoperative analgesia: various analgesia methods can be used (intravenous, epidural, nerve block sustained or self-controlled analgesia, or combined with oral medication), but both groups avoid using any sedative.

Considering the actual situation and the particularity of geriatric anesthesia, it is estimated that there will be some differences in the implementation of anesthesia, puncture technique, and intraoperative management among the research centers and anesthesiologists. The scheme does not provide for these differences or differences.

8. Main indicators:

Incidence of delirium within 7 days after surgery (CAM)

9. Secondary indicators:

- 1) Delirium type, severity, duration (diagnosed by DRS-R-98 scale)
- 2) Postoperative pain score VAS pain score)
- 3) Other related complications and outcomes: related complications: pulmonary infection, myocardial infarction, renal failure,

gastrointestinal bleeding;

- 4) Hospitalization time
- 5) The mortality rate during hospitalization and 30 days after surgery
- 6) The total cost of hospitalization and anesthesia.
- 7) 6 months and 1-year follow-up: incidence, type, severity, the cognitive function of delirium (mini-mental state examination, MMSE), quality of life (The MOS 36-item Short-Form Health Survey, SF-36) Hospital Anxiety and depression scale, HADS mental state), mortality.

Description:

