2.2 Objectives

This clinical trial is pragmatic, multicentre, prospective, parallel grouped, randomised controlled. The RAGA trial aims to determine whether different types of anaesthesia (regional anaesthesia vs general anaesthesia) given to older patients undergoing hip fracture surgery result in the equivalent incidence of postoperative delirium.

This will be met through meeting the following aims (as specified in the protocol):

- Aim 1: To assess whether there are differences in the incidence of postoperative delirium in different groups (by age, existing cognitive impairment, or preoperative delirium) between groups;

- Aim 2: To compare the subtypes, severity, and duration of postoperative delirium between the anaesthesia groups;
- Aim3: To describe the pain scores in the postoperative period either regional anaesthesia or general anaesthesia;
- Aim4: To compare the occurrence of non-delirium complications between the groups;
- Aim 5: Assessment of the length of hospital stay between groups;
- Aim 6: Assessment of the mortality during the hospital stay and the follow-up period after hospital admission between groups;
- Aim 7: Assessment of the cognitive and functional decline and quality of life on 30 days, 6 months, and 12 months after surgery between groups.
- Aim 8: To assess the cost-effectiveness of using regional anaesthesia compared to general anaesthesia in terms of total in-hospital costs and expenditure of anaesthesia.

3. Study Methods

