3.1 Trial Design

This clinical trial is pragmatic, multicenter, prospective, parallel grouped, randomised controlled with cost-effective analysis. Participants will be randomised in a 1:1 ratio to regional anaesthesia or general anaesthesia.

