4.1 Confidence Intervals and p-values

All estimates of differences between groups would be presented with two-sided 95% confidence intervals unless otherwise stated. Statistical significance will be considered if $p < 0.05$ (two-sided).

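### The SAP promises a cost comparison but states no method for it, and the only rule that reaches costs, the protocol's normality test then rank-sum test, does not estimate a mean cost difference

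*Protocol*

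**What the plan says.** **Costs are promised.** Protocol section 9 lists as a secondary indicator "The total cost of hospitalization and anesthesia", and the fourth research question at the end of Protocol section 1 asks about medical expenses and economic benefit. In the SAP, Aim 8 (2.2) is "To assess the cost-effectiveness of using regional anaesthesia compared to general anaesthesia in terms of total in-hospital costs and expenditure of anaesthesia". SAP 3.1 describes the trial as "parallel grouped, randomised controlled with cost-effective analysis". SAP 7.2 lists "Economic parameters, including total cost in hospital and expenditure for anesthesia and resource using costs" among the secondary outcomes and classes them as variables "which are the continuous variables".

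**No method is given for them.** SAP 8.2 has entries SO1 to SO5. Delirium duration (SO2), pain (SO3) and length of stay (SO5) get generalised linear models, and the list stops there. The general modelling statement in SAP 4.2 names only a log-binomial model, which cannot be fitted to a cost.

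**What is left is generic.** Protocol 12.4.3 covers all measurement data: "First, the normal test is carried out". Data that pass go to t-tests, analysis of variance or covariance analysis. For the rest, "rank-sum test, paired rank-sum test, H test and so on are used for the data that do not conform to normal distribution". Neither document mentions a mean cost difference, a bootstrap, a model for costs or an incremental cost-effectiveness ratio.

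**The concern.** The economic question is about money spent, which is mean cost multiplied by the number of patients. Cost-effectiveness likewise needs a difference in mean cost. A rank-sum test compares orderings. It does not register how expensive the most expensive patients are, although they drive total spending, and it returns no mean difference.

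Suppose one technique is slightly cheaper for most patients and much dearer for a few. The rank-sum test can then favour it although average spending is the same. The converse also occurs: two arms with equal medians but different mean costs can look alike to the test.

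Choosing the test from the outcome data also adds a data-driven step that a cost line fixed in advance would avoid. At stake is one named aim of the trial.

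**Working it through.** **Inputs from the documents.** 1,000 patients, 1:1 allocation, 10% drop-out (SAP 3.2, 3.3): 1000 × 0.90 / 2 = 450 per arm. Two-sided 5% level. The plan gives no figure for costs. Its one sample-size figure, 441 per group for 26% v 18.2%, reproduces: (1.960 + 0.842)² × (0.26×0.74 + 0.182×0.818) / 0.078² = 440.3, rounded up to 441. It does not bear on costs.

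**Assumptions, not from the documents.** Log-normal costs, log SD 0.5 unless stated; equal true mean costs in both arms; at least 2,000 simulated trials per scenario.

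**Step 1: which branch applies?** Shapiro-Wilk rejected normality in every simulated sample checked (200 to 300 per scenario, log SD 0.3 to 0.5). The protocol does not name its normality test. With skew of this order the rule leads to the rank-sum branch.

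**Step 2: matching shapes.** With log SD 0.5 in both arms and 441 per arm, the rank-sum test rejects in 5.3% of trials and the Welch t-test in 5.4%. There is no excess error.

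**Step 3: costly tail in the regional arm only, 450 per arm.** A share 1−f of regional patients cost a fraction s less. The share f cost m times as much, with m = (1 − (1−f)(1−s)) / f so that the means are equal. For s = 0.10 and f = 0.05, m = (1 − 0.95×0.90)/0.05 = 2.90.

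| s | f | m | Rank-sum declares regional cheaper |
|---|---|---|---|
| 0.10 | 0.05 | 2.90 | about 44% |
| 0.08 | 0.05 | 2.52 | 24–27% |
| 0.15 | 0.10 | 2.35 | 60–62% |
| 0.10 | 0.10 | 1.90 | 19–21% |

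Ranges are across repeat runs. The Welch test rejected in 4.4% to 5.8%.

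**Step 4: tail in both arms.** The general arm has 5% of patients at 2.9 times cost; the regional tail share varies, and the cost of the other regional patients is set so that means stay equal. With 5% in both arms, regional is declared cheaper in about 2–3% (nominal in one direction: 2.5%). As the regional share rises from 6% to 10%, the figure rises from about 5% to about 40% if the tail cost is the same absolute amount in both arms. It rises from about 4% to about 20% if the tail is 2.9 times the regional arm's own lower base cost.

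**Step 5: a different mechanism.** Equal means, unequal log SD, 441 per arm. The rank-sum test rejects in 31% (0.5 v 0.6), 81% (0.5 v 0.7), 99% (0.5 v 0.8), 80% (0.4 v 0.6) and 29% (0.3 v 0.4). Welch stays at 4.6% to 5.7%.

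**Step 6: the converse.** Equal medians, log SD 0.5 v 0.6, 0.7 and 0.8, so that means differ by 5.7%, 12.7% and 21.5%. The rank-sum test rejects in about 5% each time; Welch rejects in 27%, 74% and 97%.

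**The case against.** The strongest reply is that nobody has planned a rank-sum test for costs. Protocol 12.4.3 is a generic rule that never mentions them. It has a branch that compares means, its list of rank tests is open-ended, and it names covariance analysis for measurement data in the pooled multicentre efficacy analysis. The SAP has moved away from the protocol's methods elsewhere and uses GLM for three other continuous outcomes, so an analyst might well extend GLM to costs. All of this stands. A reader might infer that the rank-sum test is the stated cost method, or is certain to be run; the documents do not support that. They support a narrower statement: no cost method is stated, and the one rule that reaches costs is unsuitable if followed. Whether the covariance line reaches costs is unclear, because it concerns efficacy. Nothing in SAP 8.2 extends GLM to costs.

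A reader might also infer a breach of SAP 4.1, which says "All estimates of differences between groups would be presented with two-sided 95% confidence intervals unless otherwise stated". That does not follow: it does not ask for a mean difference, and a rank-based shift with a CI would satisfy it.

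Finally, the large error rates depend on shapes that differ between arms. Complications and intensive care can occur in either arm. Of the obvious sources of a costly tail, only conversion to general anaesthesia (Protocol section 7, item 4) is specific to the regional arm. Anaesthesia expenditure, defined in SAP 5.2 through drugs and labour, need not have such a tail at all. This stands too, and step 4 shows how far it matters.

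**Conclusion.** The point holds as an omission with a poor default. The SAP promises a cost and cost-effectiveness comparison and specifies no cost analysis. The only rule left would send skewed costs to a test that neither estimates nor tests a difference in mean cost. That part does not depend on any simulation.

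The risk of a misleading result is conditional. It is absent when the two cost distributions have the same shape. It is about 20% to 60% in the illustrative cases with a costly tail in the regional arm only, and much smaller when both arms have similar tails. With unequal log SDs the range was 29% to 99%. None of these is an estimate for this trial, because the documents contain no cost data.

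Costs are a secondary outcome. The delirium comparison and its conclusion are untouched. The change is still worth making, because a named aim currently has no suitable analysis.

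**What to change.** Add a cost line to SAP 8.2, fixed in advance, covering total in-hospital cost and anaesthesia cost separately:

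- Estimate the difference in arithmetic mean cost between arms with a bootstrap 95% CI. A gamma GLM reported as a mean difference is an alternative, in line with the GLM already used for SO2, SO3 and SO5.
- Report median and IQR as description only.
- State that the normality-test rule of Protocol 12.4.3 does not apply to the cost outcomes.

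This supplies the cost side only. If Aim 8 is meant to yield a cost-effectiveness measure, such as an incremental ratio, that needs its own sentence; otherwise the aim should be worded as a cost comparison.

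The cost is SAP wording: no new data, patients or procedures. The downside is a wider CI when tails are heavy, which reflects the real uncertainty about mean spending.
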